## 7.7 Expedited Reporting

### **Reporting to the Data and Safety Monitoring Committee**

If a death occurs during the treatment phase of the study or within 30 days after the last administration of the study drug(s) and it is determined to be related either to the study drug(s) or to a study procedure, the Investigator or his/her designee must notify the DSMC Chair (or qualified alternate) within 1 business day of knowledge of the event. The contact may be by phone or e-mail.

### **Reporting to UCSF Committee on Human Research (Institutional Review Board)**

The Principal Investigator must report events meeting the UCSF IRB definition of “Unanticipated Problem” (UP) within 10 business days of his/her awareness of the event.

### **Expedited Reporting to the Food and Drug Administration**

If the study is being conducted under an IND, the Sponsor-Investigator is responsible for determining whether or not the suspected adverse reaction meets the criteria for expedited reporting in accordance with Federal Regulations (21 CFR §312.32).

The Investigator must report in an IND safety report any suspected adverse reaction that is both serious and unexpected. The Sponsor-Investigator needs to ensure that the event meets all three definitions:

- Suspected adverse reaction (as defined in 6.1.30)
- Unexpected (as defined in 0)
- Serious (as defined in 6.1.5)

If the adverse event does not meet all three of the definitions, it should not be submitted as an expedited IND safety report.

The timeline for submitting an IND safety report to FDA is no later than **15 calendar days** after the Investigator determines that the suspected adverse reaction qualifies for reporting (21 CFR 312.32(c)(1)).

Any unexpected fatal or life-threatening suspected adverse reaction will be reported to FDA no later than **7 calendar days** after the Investigator’s initial receipt of the information (21 CFR 312.32(c)(2)).

Any relevant additional information that pertains to a previously submitted IND safety report will be submitted to FDA as a Follow-up IND Safety Report without delay, as soon as the information is available (21 CFR 312.32(d)(2)).

### **Reporting to Pharmaceutical Companies providing Study Drug**

To ensure patient safety, every SAE, regardless of suspected causality, occurring after the patient has provided the main informed consent and until at least 30 days after the patient has stopped study treatment must be reported to Novartis within 24 hours of learning of its occurrence.

Any SAEs experienced after this 30 days period should only be reported to Novartis if the investigator suspects a causal relationship to the study treatment. Recurrent episodes, complications, or progression of the initial SAE must be reported as follow-up to the original episode within 24 hours of the investigator receiving the follow-up information. An SAE occurring at a different time interval or otherwise considered completely unrelated to a previously reported one should be reported separately as a new event.

Information about all SAEs is collected and recorded on the Serious Adverse Event Report Form; all applicable sections of the form must be completed in order to provide a clinically thorough report. The investigator must assess and record the relationship of each SAE to each specific study treatment (if there is more than one study treatment), complete the SAE Report Form in English, and send the completed, signed form by fax within 24 hours to the oncology Novartis Drug Safety and Epidemiology (DS&E) department - [contact]). The original copy of the SAE Report Form and the fax confirmation sheet must be kept with the case report form documentation at the study site.

Follow-up information is sent to the same contact(s) to whom the original SAE Report Form was sent, using a new SAE Report Form stating that this is a follow-up to the previously reported SAE and giving the date of the original report. Each re-occurrence, complication, or progression of the original event should be reported as a follow-up to that event regardless of when it occurs. The follow-up information should describe whether the event has resolved or continues, if and how it was treated, whether the blind was broken or not, and whether the patient continued or withdrew from study participation.

If the SAE is not previously documented in the Investigator's Brochure or Package Insert (new occurrence) and is thought to be related to the Novartis study treatment, an oncology Novartis Drug Safety and Epidemiology (DS&E) department associate may urgently require further information from the investigator for Health Authority reporting. Novartis may need to issue an Investigator Notification (IN), to inform all investigators involved in any study with the same drug that this SAE has been reported. Suspected Unexpected Serious Adverse Reactions (SUSARs) will be collected and reported to the competent authorities and relevant ethics committees in accordance with Directive 2001/20/EC or as per national regulatory requirements in participating countries.

### **Pregnancies**

To ensure patient safety, each pregnancy occurring while the patient is on study treatment must be reported to Novartis within 24 hours of learning of its occurrence. The pregnancy should be followed up to determine outcome, including spontaneous or voluntary termination, details of the birth, and the presence or absence of any birth defects, congenital abnormalities, or maternal and/or newborn complications.

Pregnancy should be recorded on a Clinical Trial Pregnancy Form and reported by the investigator to the oncology Novartis Drug Safety and Epidemiology Department (DS&E). Pregnancy follow-up should be recorded on the same form and should include an assessment

of the possible relationship to the study treatment any pregnancy outcome. Any SAE experienced during pregnancy must be reported on the SAE Report Form.

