16. Women of childbearing potential must have a negative serum or urine pregnancy test within 3 days prior to study enrollment. The effects of trametinib on the developing human fetus are unknown. For this reason and because animal studies with trametinib have shown reproductive toxicity, women of child-bearing potential and men must agree to use effective methods of contraception (hormonal or barrier method of birth control) prior to study entry, for the duration of study participation, and for 4 months following discontinuation of trametinib. Should a woman become pregnant or suspect she is pregnant while she or her partner is participating in this study, she should inform her treating physician immediately. Men treated or enrolled on this protocol must also agree to use adequate contraception prior to the study, for the duration of study participation, and 4 months after completion of study drug administration.
17. Able to swallow and retain orally administered medication and does not have any clinically significant gastrointestinal abnormalities that may alter absorption such as malabsorption syndrome or major resection of the stomach or bowels.
18. All prior treatment- related toxicities must be CTCAE (Version 4.03) ≤ Grade 1 (except alopecia) at the time of randomization
19. Ability to understand a written informed consent document, and the willingness to sign it.

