### 6.1.3 End-of-Treatment Study Procedures

To be completed within 30 days of the last dose of study drug.

- Disease assessment including imaging (CT or MRI) of chest/abdomen/pelvis, and brain (if lesions found in screening), for tumor/lesion assessment
- Physical examination
- Vital signs
- Performance Status
- Evaluation of adverse events
- Concomitant medications
- Hematology labs (other than CBC with diff)
- Complete blood count (CBC) with differential and platelet count
- Blood chemistry assessment, including:
  - Alkaline phosphatase, ALT/AST, total bilirubin, calcium, phosphorus, BUN, creatinine, total protein, albumin, fasting glucose, potassium, sodium, chloride, bicarbonate,
  - Coagulation assessment, including PT/PTT/INR
- Urinalysis
- Electrocardiogram (ECG)
- Blood collection for ctDNA and cfDNA biomarkers
- Optional tumor biopsy for biomarker analysis and exploratory studies.

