| Laboratory proceduresg |                        |                  |           |           |            |            |                           |           |           |            |            |                        |                  |            |
| CBC w/ Diff                              | X                      | X                |           |           |            |            | X                         |           |           |            |            | X                      | X                |            |
| Blood chemistry                          | X                      | X                |           |           |            |            | X                         |           |           |            |            | X                      | X                |            |

| Period/Procedure                     | Screening a | Cycle 1   |           |            |            |            | Cycle 2 and future Cycles |           |            |            |            | End of Treatment visit            | Follow-up visits            |
|--------------------------------------|------------------------|-----------|-----------|------------|------------|------------|---------------------------|-----------|------------|------------|------------|-----------------------------------|-----------------------------|
| Study Day/Visit Day                  | -28 to 0 (+/- 3)       | 1 (+/- 3) | 8 (+/- 3) | 15 (+/- 3) | 22 (+/- 3) | 29 (+/- 3) | 1 (+/- 3)                 | 8 (+/- 3) | 15 (+/- 3) | 22 (+/- 3) | 29 (+/- 3) | 30d after last dose of study drug | FU every 3 months (+/- 14d) |
| Coagulation                          | X                      | X         |           |            |            |            | X                         |           |            |            |            | X                                 | X                           |
| Urinalysis                           | X                      | X         |           |            |            |            | X                         |           |            |            |            | X                                 |                             |
| Pregnancy test (HCG)                 | X                      | X         |           |            |            |            | X                         |           |            |            |            |                                   |                             |

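### Section 7.7 requires pregnancies to be reported and followed only if they occur on treatment, so conceptions in the protocol's own 4-month post-treatment contraception period fall under no reporting rule, and partner pregnancies are not expressly covered

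*Combined protocol and SAP*

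**What the plan says.** - **Reporting (Section 7.7, Pregnancies).** The rule is that "each pregnancy occurring while the patient is on study treatment must be reported to Novartis within 24 hours", counted from when the pregnancy becomes known. The next sentence sets the follow-up duty: "The pregnancy should be followed up to determine outcome, including spontaneous or voluntary termination, details of the birth". No post-treatment period is given, and partners are not mentioned.
- **Contraception (Section 3.3.1, inclusion criterion 16).** Fetal effects in humans are described as unknown, and animal studies as showing reproductive toxicity. Women of childbearing potential and men must use contraception before entry, "for the duration of study participation, and for 4 months following discontinuation of trametinib". The requirement is repeated for men: "Men treated or enrolled on this protocol must also agree to use adequate contraception prior to the study", and then "for the duration of study participation, and 4 months after completion of study drug administration". The same criterion tells a woman to inform her treating physician if she becomes pregnant during her own or her partner's participation.
- **SAEs (Section 7.7).** All SAEs go to the drug supplier from consent until at least 30 days after treatment stops. After that, only those with suspected causality do.
- **Testing (Sections 6.1.1 to 6.1.4, Table 6.1).** Pregnancy tests are listed at screening, Cycle 1 Day 1, and Cycle 2 onward. None is listed at the end-of-treatment visit ("To be completed within 30 days of the last dose of study drug") or at follow-up visits.

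**The concern.** The protocol treats the months after the last dose as a period in which pregnancy should be avoided because of possible fetal harm, yet its pregnancy rule stops with treatment. Outcome follow-up (losses, birth defects, newborn complications) begins only once a pregnancy falls under that rule. A site that follows the text exactly has no duty to report or follow a conception in the period that the contraception rule singles out. Any fetal-safety information from such a pregnancy could be lost. For male patients the text also leaves open whether a partner's pregnancy counts at all.

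**Working it through.** The plan states no figure to reproduce. The check sets the windows side by side and then asks whether another rule closes the gap.

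**1. Length of the windows after the last dose**

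| Rule | Source | Days after last dose |
|---|---|---|
| Pregnancy report and outcome follow-up | Section 7.7 | 0 |
| All SAEs, any causality | Section 7.7 | at least 30 |
| Contraception, women and men | Inclusion criterion 16 | 4 months |

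Taking a month as 28 to 31 days, 4 × 28 = 112 and 4 × 31 = 124. The contraception period therefore exceeds the pregnancy-reporting window by 112 to 124 days. The part that also lies beyond the 30-day all-SAE window is 112 − 30 = 82 to 124 − 30 = 94 days.

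**2. Does another rule close the gap?**

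- *SAE criteria.* Section 7.3.2.3 and Appendix 4 (3.2) list congenital anomaly or birth defect, but not pregnancy. A defect after a post-treatment conception would normally come to light after day 30, when a report depends on suspected causality. It also depends on someone learning the outcome of a pregnancy that nobody is required to follow. Appendix 4 further lets the Principal Investigator class any event as serious, which is a discretion and not a requirement.
- *Notice to the physician.* Inclusion criterion 16 ties this to participation, not to the 4 months. It leads to no named report, form or follow-up.
- *Visits.* Section 3.5 sets 30 days of follow-up. Section 6.1.4 schedules 3-monthly visits for up to 18 months after enrollment or until progression. Progression is itself a reason to stop treatment (Section 3.4), so patients who stop for that reason are outside those visits.

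None of these requires a post-treatment conception to be reported or followed.

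**3. How much drug remains?** Section 1.2.3 gives a terminal half-life of 5.3 days, measured after a single dose. Assuming first-order decline at that rate, the fraction of the end-of-treatment level left at day t is 2^(−t/5.3).

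- Five half-lives: 5 × 5.3 = 26.5 days.
- Day 30: 2^(−30/5.3) ≈ 0.020, or about 2%.
- Day 120: 2^(−120/5.3) ≈ 1.5 × 10⁻⁷.

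Some drug is therefore present for the first weeks after reporting ends. For the later part of the 4 months, the case rests on the protocol's own contraception period and not on plasma level.

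**4. Detection.** The end-of-treatment visit includes blood tests and urinalysis but no pregnancy test, in both Section 6.1.3 and Table 6.1. A conception after the last on-treatment test is not looked for at that visit.

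**The case against.** A contraception precaution and a reporting duty serve different purposes and need not be equally long, so the mismatch is a design choice and not a formal contradiction. The backstops above are real, if partial. For a patient who stops without progression, participation may outlast dosing, which extends the notice to the physician and brings visits with adverse-event evaluation. Consent pages and the pregnancy form are not in the reviewed text and may carry instructions to patients.

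Most of this is fair. It limits the point without removing it: the protocol gives no reason for ending pregnancy reporting with the last dose while the SAE window and the contraception period both run on, and no backstop creates a duty to report or follow.

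Four stronger readings are tempting, and the documents do not support them:

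- *A pregnancy first recognised after stopping escapes the rule.* It does not if it began on treatment, because the 24-hour clock runs from learning of it. For these pregnancies the weakness is detection, not reporting.
- *Partners are excluded.* The rule speaks of each pregnancy and does not limit this to patients, so for men on treatment the text is ambiguous. Inclusion criterion 16 already has a pregnant partner notify her physician during participation.
- *These pregnancies will go unreported.* The supportable statement is that they are not required to be reported.
- *Every conception in the 4 months is a serious exposure.* The half-life calculation does not support that for most of the period.

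**Conclusion.** The point holds as a gap in the reporting window. A pregnancy conceived in the 4 months after the last dose, in a patient or in a male patient's partner, is not required to be reported or followed anywhere in the documents. During treatment, coverage of partners is unclear. The missing end-of-treatment test is confirmed but secondary.

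The window lengths measure the uncovered period and are not an estimate of events. The documents give no pregnancy rate. With 27 patients planned, few if any cases are expected. Sample size, alpha, power and the ORR analysis are not touched. The conclusion assumes that the removed consent pages and the unseen pregnancy form contain no reporting duty that the protocol itself omits. The sponsor should make the change because it is cheap and outcome data that nobody collects may not be recoverable.

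**What to change.** Reconcile Section 7.7 with inclusion criterion 16:

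1. Extend pregnancy reporting and outcome follow-up in Section 7.7 to the end of the protocol's own post-treatment contraception period, or state and justify a different end point.
2. State expressly in Section 7.7 that pregnancies in partners of male patients are included.
3. Secondarily, reconcile the absence of a pregnancy test in Section 6.1.3 and in the end-of-treatment column of Table 6.1 with that period: either schedule one or say why it is not needed.

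Items 1 and 2 need about one sentence. If a test is added, Section 6.1.3 and one cell of Table 6.1 change, and blood and urine are already collected at that visit. The running cost is a few extra reports at most, and consent from partners where their pregnancy is followed. The main limitation is practical: once visits end, especially after progression, the rule depends on patients volunteering the information.

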#### Warnings and precautions

Additional safety information collected between IB updates will be communicated in the form of Investigator Notifications. This information will be included in the patient informed consent and should be discussed with the patient during the study as needed

## 8 Statistical Considerations and Evaluation of Results

### 8.1 Study Endpoints

See Section 2.4 for study endpoints.

This is a Phase II, open-label, multicenter clinical trial evaluating the efficacy and safety of trametinib monotherapy in patients with advanced non-squamous NSCLC whose tumors harbor a non-synonymous *NF1* mutation and are wildtype for KRAS. Patients will receive trametinib monotherapy in 28 day cycles.

#### 8.1.1 Randomization

This is a single-arm, open-label phase II study without any randomization.

#### 8.1.2 Unblinding Subjects

Study is open-label so unblinding subjects is not applicable.

#### 8.1.3 Stratification Factors

None

### 8.2 Determination of Sample Size and Accrual Rate

#### 8.2.1 Sample Size and Power Estimate

The primary endpoint is objective response rate (ORR). To provide 80% power to detect a 30% ORR compared to the null hypothesis of a 10% ORR in each cohort, 27 patients will be enrolled, with the goal of obtaining 24 evaluable patients. Using a Simon 2-stage design, if we do not observe at least 2 responses within the first 15 patients, enrollment will be stopped due to lack of efficacy.

The primary efficacy analysis will be based on one-sided exact binomial test comparison of the observed ORR in patients receiving at least one dose of study treatment to the null-hypothesized value of 10%, using the 5% significance level. Secondary time-to-event endpoints (DR, PFS and OS) will be summarized using Kaplan-Meier estimates with associated 95% confidence limits. The secondary DCR endpoint will be summarized as a proportion with an exact binomial 95% confidence interval. Safety analyses will be descriptive summaries of AEs by patient and type.

## 8.2.2

### Replacement Policy

All patients who receive a dose of trametinib will be analyzed for safety and efficacy. Subjects who discontinue from study participation prior to receiving any dose of study therapy may be replaced after discussion with the Principal Investigator. Patients removed from study for unacceptable treatment related adverse event(s) will be followed until resolution or stabilization of all treatment related AEs to grade 2 or lower; however, they will not be replaced.

## 8.2.3

### Accrual estimates

At UCSF, UC Davis, and UC San Diego we see > 200 patients per month with advanced NSCLC, 80% of whom have non-squamous histology. Based on The Cancer Genome Atlas (TCGA) Research Network studies described in Section 1.1, we predict that about 11% of lung adenocarcinomas will harbor *NF1* mutations. Conservatively, we expect that 10 patients per month will harbor one of these mutations and that 1-2 patients per month will be eligible and will consent to participate in the study.

#### Interim Analyses and Stopping Rules

Using a Simon 2-stage design, if we do not observe at least 2 responses within the first 15 patients in a given cohort, enrollment to that arm would be stopped due to lack of efficacy.

## 8.3 Analyses Plans

### 8.3.1 Analysis Population

All patients who receive a dose of trametinib will be analyzed for safety and efficacy. Subjects who discontinue from study participation prior to receiving any dose of study therapy may be replaced after discussion with the investigator sponsor. Subjects who have received any dose of study therapy will not be replaced.

Demographic and baseline characteristics will be summarized by each cohort and overall. In general, frequency distribution and percentage will be used to summarize categorical measurements, while mean with standard deviation and median with interquartile range will be used to describe symmetric and skewed continuous measurements, respectively. Univariate analysis among variables will be assessed using the two-sample t-test, Wilcoxon-rank-sum test, Chi-square test, as appropriate.

### 8.3.2 Primary Analysis (or Analysis of Primary Endpoints)

The ORR is defined as the best overall response recorded from the start of the treatment until disease progression or recurrence as assessed over a 1-year period from the start of treatment. The frequency and percentages of patients with a best overall response rate of complete response (CR), partial response (PR), stable disease (SD), or progressive disease (PD) will be determined. We will test the hypothesis that the ORR is greater than the null hypothesis of 10% using the Fisher's exact test.

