### 8.3.3

## Secondary Analysis (or Analysis of Secondary Endpoints)

### Definition and analytical plan for secondary efficacy endpoints:

**(a) Duration of response (DR):** The DR for CR and PR will be measured from the date that the best response is first recorded until the date that PD is documented over the period of 1 year. For patients who continue treatment post progression, the date of PD documentation will be used for analysis. The DR will be summarized using descriptive statistics (N, mean, standard deviation, minimum, and maximum).

**(b) Disease control rate (DCR):** DCR will be defined as the percentage of patients who have achieved CR, PR, or SD for at least 12 weeks. The DCR will be summarized using descriptive statistics (N, mean, standard deviation, minimum, and maximum).

**(c) Progression-free Survival (PFS):** PFS will be calculated as 1+ the number of days from the first dose of study drugs to documented radiographic progression or death due to any cause over a period of 1 year. For patients who continue treatment post-progression, the date of radiographic progression will be used for PFS analysis. The Kaplan-Meier analysis will be used to calculate the median PFS with 95% confidence interval.

**(d) Overall Survival (OS):** OS will be calculated as 1+ the number of days from the first dose of study drugs to death due to any cause over a period of 1 year. The Kaplan-Meier analysis will be used to calculate the median OS with 95% confidence interval.

**(3) Definition and analytical plan for safety and tolerability endpoints:** The safety population will consist of all subjects who receive any amount of study treatment. Safety will be assessed by evaluation of AEs. All safety analyses will be performed using the safety population. Adverse event terms recorded on the CRFs will be mapped to preferred terms using the Medical Dictionary for Regulatory Activities (MedDRA). Seriousness, severity grade and relationship to study treatment will be assessed by the investigator. Severity grade will be defined by the National Cancer Institute (NCI) CTCAE v4.03. Listings of AEs will be provided.

Separate tables will present the following by dose group and study phase:

- All treatment-emergent AEs
- Treatment-emergent AEs by CTCAE grade
- Grade 3 or greater treatment-emergent AEs
- Treatment-related, treatment-emergent AEs
- Dose-limiting toxicity AEs
- Serious treatment-emergent AEs
- Treatment-emergent AEs with an outcome of death

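### Section 8.3 contradicts Section 8.2.1: duration of response has two different summaries and no rule for responders without progression, and the primary test carries the wrong label

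*Combined protocol and SAP*

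**What the plan says.** **DR.** Section 8.2.1: "Secondary time-to-event endpoints (DR, PFS and OS) will be summarized using Kaplan-Meier estimates with associated 95% confidence limits". Section 8.3.3(a): "The DR will be summarized using descriptive statistics (N, mean, standard deviation, minimum, and maximum", with DR "measured from the date that the best response is first recorded until the date that PD is documented over the period of 1 year". Items (c) and (d) of 8.3.3 name Kaplan-Meier for PFS and OS; item (a) does not. The 1-year limit on DR is absent from Sections 2.4.2 and 7.1.1.3.

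**DR start.** Section 7.1.1.3 (Duration of overall response) starts the clock at the first CR or PR. Sections 2.4.2 and 8.3.3(a) start it when the best response is first recorded.

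**Primary test.** Section 8.2.1 specifies a "one-sided exact binomial test comparison of the observed ORR in patients receiving at least one dose of study treatment" against 10% at the 5% level. Section 8.3.2 says: "We will test the hypothesis that the ORR is greater than the null hypothesis of 10% using the Fisher's exact test". Section 8.1.1 says: "This is a single-arm, open-label phase II study without any randomization".

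**DCR.** Section 8.2.1 gives a proportion with an exact binomial 95% interval. Section 8.3.3(b) gives N, mean, SD, minimum and maximum.

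**Follow-up.** The Abstract says 12 months for all patients (Duration of Follow up), and scanning until progression for those who stop trametinib without it (Efficacy Assessments). Section 3.5 says 30 days after treatment. Section 6.1.4 says every 3 months, up to 18 months after enrollment or until progression.

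**The concern.** An analyst who opens the section on primary and secondary analyses finds instructions that differ from those in the sample-size section.

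For DR this can change a reported result. DR ends at documented progression, so a responder without progression inside the year has no end date. A mean needs a number for every patient, and 8.3.3(a) does not say what number to use. If such responders are left out, the longest responses are the ones lost. It is also unstated whether the year runs from response or from the start of treatment.

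For the primary endpoint, the named test compares two observed groups. Here there is one group and a fixed 10%, so the test cannot be run as written.

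**Working it through.** **Primary test.** Inputs from Section 8.2.1: null 10%, alternative 30%, 5% one-sided, 24 evaluable of 27 enrolled, continue with at least 2 responses in the first 15. The plan states 80% power but no final cut-off. The p-value for x responses is P(X ≥ x) with X ~ Bin(n, 0.10).

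| n | p at 5 responses | p at 6 responses |
|---|---|---|
| 24 | 0.085 | 0.028 |
| 25 | 0.098 | 0.033 |
| 26 | 0.112 | 0.040 |
| 27 | 0.127 | 0.047 |

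So the cut-off is 6 or more for every n from 24 to 27. Two-stage power with that cut-off is the sum over x = 2 to 15 of P(X1 = x) × P(X2 ≥ 6 − x), where X1 ~ Bin(15, 0.30) and X2 ~ Bin(n − 15, 0.30). It is 76.8% at n = 24, 80.2% at 25 and 85.5% at 27. These values bracket the stated 80%, so the sample size fits the 8.2.1 test. Fisher's test needs a 2×2 table. The documents supply one row and a constant, so there is nothing to compute.

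**DR summary.** The documents give no expected DR, so these are assumptions: exponential DR with true median M of 3, 4, 6 or 12 months; progression detected only at scans every 8 weeks after response (8 × 7 / 30.44 = 1.84 months); everyone scanned to the end of the window; no deaths without progression.

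If the year runs from response, six scans fall inside it, the last at 6 × 1.84 = 11.04 months. With scan times t_j = 1.84j:
- Share progressing at scan j: p_j = 2^(−t_(j−1)/M) − 2^(−t_j/M).
- Share without progression: s = 2^(−11.04/M).
- Mean if they are dropped: D = Σ t_j p_j / (1 − s).
- Mean if they are counted to the last scan: (1 − s)D + 11.04s.
- Mean if they are capped at the year: (1 − s)D + 12s.

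For M = 12: s = 0.5285 and D = 5.87. The last-scan mean is 0.4715 × 5.87 + 0.5285 × 11.04 = 8.60. The capped mean is 2.77 + 6.34 = 9.11.

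| True median | s | Mean, dropped | Mean, to last scan | Mean, capped at 12 | Dropped vs last scan | Dropped vs cap |
|---|---|---|---|---|---|---|
| 3 | 8% | 4.4 | 4.9 | 5.0 | −11% | −12% |
| 4 | 15% | 4.8 | 5.7 | 5.9 | −16% | −18% |
| 6 | 28% | 5.3 | 6.9 | 7.2 | −23% | −26% |
| 12 | 53% | 5.9 | 8.6 | 9.1 | −32% | −36% |

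If the year runs from treatment start and response is seen at the 8-week scan, 12 − 1.84 = 10.16 months remain, with five scans, the last at 9.20 months. The dropped mean is then 13% to 32% below the last-scan mean and 15% to 37% below the capped mean.

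**Is the Kaplan-Meier median reached?** At the 30% alternative, about 0.30 × 27 = 8 patients respond. The median is reached if at least 4 of 8 progress in the window. On the same assumptions and a true median of 3, 4, 6 or 12 months, the probability is over 99.9%, 99.7%, 96% and 57% (year from response), or 99.9%, 99%, 90% and 43% (year from treatment start).

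**DR start.** The two rules agree unless a PR later becomes a CR. If the CR is seen at the next scan, the best-response rule shortens DR by one interval: 8 weeks, or 6 to 10 weeks with the ±1 week window on each scan. The documents give no frequency.

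**DCR.** The mean of a 0/1 variable is the proportion p, and its SD follows from p alone, as √(p(1 − p)). Section 8.3.3(b) therefore loses only the confidence interval.

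**The case against.** The strongest reply is that little here can change a conclusion. Section 8.3.2 already has a direction and a fixed null, and only one of the two named tests can be run on a single arm. That stands.

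A reader might infer something stronger: with a comparator responding at about 10%, Fisher's test would demand more than 6 responses, so the trial could pass under one section and fail under the other. The documents do not support this. They name no comparator, and any such threshold depends wholly on a group size the reader invents. Leftover multi-group wording does not supply one. The stopping rule says "in a given cohort, enrollment to that arm would be stopped due to lack of efficacy", and Section 8.3.1 says "Demographic and baseline characteristics will be summarized by each cohort and overall", but Section 8.2.1 also refers to cohorts. The two-sample tests in 8.3.1 could describe subgroups within the one arm.

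On DR, neither section says its summary is the only one, so both could be reported. That is fair, but it leaves the mean undefined. It can also be said that context favours treatment start as the origin: 8.3.2 uses it for ORR, and PFS and OS count from first dose. That is plausible, but the DR sentence does not say it, and the gap is of similar size under either origin.

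Nor must a plain mean choose only between dropping and capping. Counting to the last assessment is a third option. It stays close to capping when everyone is scanned to the end, and moves away from it when scanning stops early.

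**Conclusion.** The contradictions are in the current text and should be corrected. The DR summary is the part with numerical consequence: 8.3.3(a), followed as written, does not define a single result. On the stated illustration, dropping responders without progression lowers the mean by about 11% to 32% against counting them to the last scan in a year from response, and somewhat more against a 12-month cap. The direction is firm, because the longest responses are the ones removed. The percentages are not predictions: they rest on an assumed exponential DR and complete 8-week scanning, and DR is a descriptive secondary endpoint.

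The Fisher wording is a wrong label. The decision rule under 8.2.1 is unaffected. The start-date conflict touches only patients whose PR deepens to CR, and the DCR conflict is minor.

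**What to change.** - **8.3.2:** replace Fisher's exact test with the 8.2.1 test: one-sided exact binomial against 10%, 5% level, all patients with at least one dose. It helps to state that this means 6 or more responses for n from 24 to 27.
- **8.3.3(a):** report the Kaplan-Meier median with a 95% confidence interval. Start DR at the first CR or PR, as in 7.1.1.3, and align 2.4.2. Censor responders who are alive without progression at the last adequate tumor assessment. State whether death without progression is an event or is censored. State whether the 1-year window runs from response or from treatment start.
- **8.3.3(b):** report DCR as a proportion with an exact binomial 95% interval.
- **Follow-up:** reconcile the Abstract (Duration of Follow up and Efficacy Assessments), Section 3.5 and Section 6.1.4, because together they determine the last adequate assessment.

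The cost is wording, with no change in sample size. The one analytic price is that the Kaplan-Meier median may not be reached if responses are long. That would be an accurate report of the data.
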